9.5 Electrolyte Correction

At the clinic, prior to the start of therapy –a basic metabolic panel, pro-BNP, hemoglobin and hematocrit, and magnesium level will be drawn STAT to ensure that the results are back within 2 hours. Electrolytes will be replenished in accordance with established protocols (Tables 1 and 2)¹⁰. The same protocol will be utilized for electrolyte imbalances correction during the follow up visits by the visiting home nurse.

Serum Creatinine (mg/dL)	Serum Potassium Level (mEq/L)				
	< 3.1	3.1-3.3	3.4-3.6	3.7-4.0	> 4.0
< 2.0	40 mEq then 40 mEq	40 mEq then 20 mEq	40 mEq	20 mEq	-
2.0-2.8	40 mEq then	20 mEq then	20 mEq	-	-

	20 mEq	10 mEq			
> 2.8	30 mEq	20 mEq	10 mEq	-	-

* If the serum potassium is < 3 mEq/L or > 5.5 mEq/L, additional monitoring should occur within 24 hours.

Serum Creatinine (mg/dL)	Magnesium Level (mEq/L)			
	< 1.0	1.0-1.5	1.6-1.9	> 1.9
< 2.0	3 gm	2 gm	1 gm	-
≥ 2.0	2 gm	1 gm	-	-

10 OUTCOMES DETERMINATION

10.1 Efficacy Endpoints

- % weight loss between enrollment/screening compared to Post Visit #1 and Post Visit #2
- Reduction in pro-BNP between enrollment/screening compared to Post Visit #1 and Post Visit #2
- Proportion of patients requiring additional 4 days of diuresis..
- Percentage of patients alive 30 days post enrollment
- Percentage of patients without hospitalization for worsening HF within 30 days after enrollment.
- Percentage of patients without a significant HF related medical event within 30 days after enrollment.

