test. Eligible participants will be educated on device preparation, placement, removal and care in accordance with the Instructions of Use Manual. The screening phase includes evaluation of the home situation to ascertain that sufficient support is or can be made available for at home treatment as an alternative to inpatient care. In appropriate settings, lay caregiver will also be trained.

Pilot Phase.

Patients will be visited daily by Steward Home Care and Hospice for home health nursing services in accordance with standard procedures. Nursing services will include checking vitals, obtaining blood samples and evaluation for clinical improvement or worsening. The first visit will be performed within 24 hours after enrollment.

The first sc2Wear Infusor will be prepared and placed on the patient as part of the training. The patient will go home with the sc2Wear furosemide Infusor in place on the abdomen to be activated upon arrival at home. Participants will be treated with the sc2Wear furosemide Infusor daily for 3 consecutive days at home. Participants will be evaluated by the cardiology service of SEMC within 24 hours after the 3rd dose of sc2Wear furosemide. If a patient was found to have responded satisfactorily but requires additional parenteral diuretics an additional 4 days may be prescribed for a total of 7 consecutive treatments. If additional units are prescribed patients are to be evaluated the cardiology service of SEMC within 24 hours after the last dose of sc2Wear furosemide Infusor.

If the subject requires further parenteral diuresis after the 7 days of at home treatment, they will be converted to usual care at that time, which may require inpatient care. Participants will be instructed to record daily morning weights during and after treatment until the second post treatment evaluation.

Interim clinic visits and laboratory assessments may be required based on clinical considerations.

The following parameters will be studied at Baseline and follow-up treatment visits.

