	
 • Body Weight • Vital signs • HF Physical examination • Dyspnea scale • Routine laboratory panel (incl. electrolyte, pro-BNP) • Adverse events • Injection site assessment 
Participants will visit the clinic 30 ± 3 days after the start of the study for a post treatment evaluation.
 
Evaluation Phase
 
The Evaluation Phase mirrors the Pilot Phase except that attempts will be made to test pre-defined clinical care paths based on the lessons of the Pilot Phase. Up to two additional Steward Health Care sites may participate in the Evaluation Phase.

SC2WEAR TREATMENT	
Novel Furosemide Injection formulation at neutral pH, 8 mg/mL, (total dose =80 mg) administered subcutaneously by means of the sc2Wear Infusor as 30 mg over the first hour and then as 12.5 mg per hour over the subsequent 4 hours.
 
Participants will be treated for 3 sequential days with one dose of sc2Wear Furosemide Infusor (80mg) daily. It is generally recommended that the sc2Wear infusor be applied in the morning. Oral diuretics should be continued concomitantly
 
If a patient was found to have satisfactorily responded but requires additional parenteral diuretics an additional 4 days may be prescribed for a total of 7 consecutive treatments.
 
Additionally, up to three sc2Wear furosemide at home treatments may be used as authorized by the treating physician in case the patient experience worsening of heart failure from day 7 to up to 30-days after enrollment.
 
(Rescue Treatment).

NUMBER OF SUBJECTS	60 (20 in Pilot Phase, 40 in Evaluation Phase)
NUMBER OF SITES	Pilot Phase: St Elizabeth's Medical Center Evaluation Phase: Up to three hospitals in the Steward Health Care System
PARTICIPATING COUNTRIES	U.S.
SUBJECT POPULATION	Male and female patients over the age of 18 with mild to moderately decompensated heart failure not requiring hospital admission for care. Subjects may be enrolled in the study only if all inclusion criteria and none of the exclusion criteria are met.

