5 OVERALL STUDY DESIGN

This is a prospective, open-label, two-phase study to evaluate the clinical utility of subcutaneous administration of a novel furosemide formulation. In the first phase of the study (Pilot Phase), the practicality and safety of the novel in-home treatment alternative will be evaluated in 20

patients presenting with mild to moderate ADHF to the cardiology service at St Elizabeth's Medical Center, Brighton, Massachusetts (SEMC).

After completion of the first phase, representatives of the sponsor and scPharmaceuticals will convene to review the experience and results and consider any adjustments to the study or workflow before commencing the Evaluation Phase of the study in which an additional 40 patients will be recruited. Adjustments to the study procedures are subject to IRB review and approval. The Evaluation Phase may involve participation by up to three Steward Health Care System hospitals.

Participants will be treated for 3 consecutive days at home. The sc2Wear™ Furosemide Infusor therapy is intended to be performed by the patient or a lay caregiver. Patients will be homebound during the episode of care for decompensated heart failure. Steward Home Care and Hospice will visit patients daily for home health nursing services. Participants will be visited at home by a visiting nurse who will give them further teaching on the sc2Wear™ Furosemide Infusor. The visiting nurse will also be responsible for obtaining history (symptoms), physical examination (including inspecting the skin for adverse reactions related to the pump), and laboratory draws, supplementation of electrolytes as needed and administration of the dyspnea scale.

Patients will be evaluated by the cardiology service of SEMC within 24 hours of the last dose of the sc2Wear™ Furosemide Infusor. If a patient is found to have satisfactorily responded but requires additional parenteral diuretics an additional 4 days may be prescribed for total of seven consecutive treatments. If additional units are prescribed, patients will be evaluated by the cardiology service of SEMC within 24 hours of the last dose of the sc2Wear™ Furosemide infusion.

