9.3 Follow Up After Last Treatment

Subjects will be assessed in the office within 24 hours of termination of at home treatment.

Assessments will include:

- Weight, Blood pressure, Heart Rate, Respiratory Rate, Temperature
- Physical examination
- NYHA classification
- Injection site assessment
- Blood test (Sodium, chloride, potassium, bicarbonate, Bun, Creatine, magnesium, pro BNP)
- Dyspnea scale (appendix B)
- Assessment for adverse events
- Assessment for interval hospitalizations, ED visits, or unscheduled clinic visits

At this visit, the physician can decide if the treatment should be extended for four extra days (after the initial three days of therapy). If there is no interval improvement, the physician can withdraw the subjects from the trial for safety reasons. The initial follow up assessment will be included in the final analysis. Patients who show improvement with initial treatment (3 days or 3 day plus up to 4 days at home) may be offered 3 extra days of “rescue treatment” as needed within 30 days of enrollment in the trial. During the “rescue treatment” they will be evaluated daily by the visiting nurse and at follow up if they need further assessment as done during the treatment phase.

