9.4 Day 30 ± 3 Clinic Visit

At Day 30, study follow-up (+/- 3 days). Subjects will undergo the following assessment.

- Medical history
- Physical examination
- Weight, Blood pressure, Heart Rate, Respiratory Rate, Temperature
- NYHA classification

- Injection site inspection
- Blood draw (sodium, potassium, chloride, bicarbonate, Bun, Creatine, magnesium, pro-BNP)
- Current Medications
- Assessment for interval hospitalizations, ED visits, or unscheduled clinic visits
- Assessment for adverse events
- Dyspnea Scale (Appendix B)

Visiting Nursing Timeline

A week prior to the initiating of the study, the visiting nurses will be given an orientation and will be taught how to use the sc2Wear Furosemide Infusor. They will also be trained on how to use the dyspnea scale to ensure consistency of the results.

The visiting nurse will visit the participant at home within 24 hours of starting the treatment. These visits will occur on the three treatment days and an additional 4 days if it is determined that the participant needs extra days. Also participants who need an extra three days of rescue treatment during 30 days will be seen on consecutive days by the visiting nurse.

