19 APPENDICES

Appendix A. Schedule of Assessments

	Screening	Baseline	Treatment*	First Post Treatment	Second Post Treatment (if applicable)	Post-Treatment Visit
Day	0	0	Daily (3 ± 4 days)	Within 24hrs of last treatment	Within 24hrs of last treatment	30±3days after first dose
Informed Consent	X					
Pregnancy Test*	X					
Training		X				
Medical History		X				
Initial sc2Wear Treatment		X				
Weight		X	X	X	X	X
Height		X				
HF Physical Exam		X	X	X	X	X
NYHA		X		X	X	X
Baseline Labs ^a		X				
Monitoring labs ^b			X	X	X	X
Vitals Signs ^c		X	X	X	X	X
Dyspnea Scale		X	X	X	X	X
Electrolyte correction		X	X			
Injection Site Inspection			X	X	X	X
Current Medication	X	X	X	X	X	X
Adverse Events ^d		X	X	X	X	X

- * To be performed by Steward Home Care and Hospice in accordance with standard practices for homebound heart failure patients
- a. Baseline laboratory panel (Sodium, potassium, Bun, Cr, Mg, pro-BNP, Hemoglobin and Hematocrit)
- b. Monitoring laboratory panel: (sodium, chloride, bicarbonate, potassium, Bun, Cr, Mg)
- c. Vital signs: Blood pressure, heart rate, temperature, respiratory rate
- d. Adverse Events: Major Event: death, hospitalization, MACE (major adverse cardiac event); Minor: ER visit for acute decompensated heart failure (excluding study related visits), admission to SNF or similar inpatient facility

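### Appendix A omits pro-BNP from every visit after baseline although Sections 9.3 and 9.4 require it, and Post Visit #2 in the weight and pro-BNP endpoints is not tied to a visit

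*Combined protocol and SAP*

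**What the plan says.** **Endpoints.** Section 10.1 and the Synopsis set the weight endpoint as percentage "weight loss between enrollment/screening compared to Post Visit #1 and Post Visit #2" and use the same two labels for pro-BNP. Section 14 names weight loss, pro-BNP reduction and the percentage with extended treatment among the primary endpoints.

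**Follow-up pro-BNP.** Section 9.3, the office visit after treatment, lists "Blood test (Sodium, chloride, potassium, bicarbonate, Bun, Creatine, magnesium, pro BNP". Section 9.4, the Day 30 visit, lists "Blood draw (sodium, potassium, chloride, bicarbonate, Bun, Creatine, magnesium, pro-BNP". The Synopsis also names pro-BNP in the routine panel for baseline and follow-up. In Appendix A, pro-BNP appears only in the baseline panel (footnote a). The panel marked for treatment days, both post-treatment visits and Day 30 is footnote b: "Monitoring laboratory panel: (sodium, chloride, bicarbonate, potassium, Bun, Cr, Mg", and the list ends there.

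**Visits.** Appendix A has three columns after treatment: First Post Treatment, "Second Post Treatment (if applicable", and a Post-Treatment Visit at 30±3 days. Section 5 explains the conditional one: "If additional units are prescribed, patients will be evaluated by the cardiology service of SEMC within 24 hours of the last dose". The Synopsis adds two sentences that bear on the label. One is "Participants will be instructed to record daily morning weights during and after treatment until the second post treatment evaluation"; the other says that patients attend the clinic at 30 ± 3 "days after the start of the study for a post treatment evaluation".

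**The concern.** The pro-BNP endpoint needs a baseline value and at least one follow-up value. If staff draw blood according to the schedule table, the follow-up value is never obtained, and a sample that was not drawn cannot be recovered. Pro-BNP is also one of the three measures by which the Synopsis says response will be judged. Up to two further sites may join in the Evaluation Phase, so the schedule may be used by staff who did not write the protocol.

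The study is descriptive, with no comparator and no test. Its results are therefore the summaries themselves, and each depends on its time point and on who is counted. For Post Visit #2 neither is fixed. One reading is a visit at the end of an extended course, in selected patients. The other is a visit at about a month, in everyone, possibly after rescue treatment.

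**Working it through.** Section 14's only numerical claim is that 59 evaluable patients give 95% confidence of seeing an event of 5% incidence. It reproduces: 1 − 0.95^59 = 0.9515, against 0.9490 for 58 patients. It does not depend on the points below, for which the plan gives no figure.

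**Step 1. Pro-BNP, place by place**

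| Visit | Body of protocol | Appendix A |
|---|---|---|
| Baseline | Listed (9.1) | Listed (footnote a) |
| Home treatment days | Not listed (9.2) | Not listed (footnote b) |
| First Post Treatment | Listed (9.3) | Not listed (footnote b) |
| Second Post Treatment, if extended | Listed (9.3, by its title) | Not listed (footnote b) |
| Day 30 | Listed (9.4) | Not listed (footnote b) |

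Footnote b agrees with Section 9.2 for the home visits. It conflicts with the body at the three clinic visits, which are the only ones that can supply the pro-BNP endpoint.

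**Step 2. Which visit is Post Visit #2?**

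- *For the conditional visit:* Appendix A numbers two post-treatment visits, First and Second, and leaves Day 30 unnumbered. The Synopsis elsewhere calls Day 30 the final follow-up, and Section 9.4 calls it study follow-up.
- *For Day 30:* the Synopsis sentence on daily weights is addressed to participants without restriction, yet it ends at a second post-treatment evaluation that patients who are not extended would not have. The Synopsis also calls Day 30 a post treatment evaluation.
- *Post Visit #1:* First Post Treatment is the only candidate, and its column carries no condition. Section 9.3 keeps the initial follow-up assessment in the final analysis.

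**Step 3. Who is counted (extension shares assumed)**

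n under the conditional reading = 60 × share extended:

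- 20%: 60 × 0.20 = 12
- 40%: 60 × 0.40 = 24
- 60%: 60 × 0.60 = 36

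Under the Day 30 reading n is up to 60 in each case. In the pilot analysis of 20 patients, 30% extended would leave 20 × 0.30 = 6.

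**Step 4. How the estimate could move (all means assumed)**

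Take mean weight loss of 3.5% at the end of an extended course, 2.0% at Day 30 in extended patients and 2.5% at Day 30 in the others. The conditional reading gives 3.5% whatever the share extended. The Day 30 reading gives:

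- 12 extended: (12 × 2.0 + 48 × 2.5)/60 = 2.4%
- 24 extended: (24 × 2.0 + 36 × 2.5)/60 = 2.3%
- 36 extended: (36 × 2.0 + 24 × 2.5)/60 = 2.2%

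This shows only that the choice of visit can change the reported figure. It does not predict the size.

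**Step 5. The extension percentage**

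Suppose 18 of 60 are extended (30%). With 3 withdrawn for no improvement, 60 − 18 − 3 = 39 (65%) finished at day 3. With 18 withdrawn, 60 − 18 − 18 = 24 (40%) finished. The endpoint is 30% both times. It is correct in both cases but says nothing about how the remaining 42 divide.

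**The case against.** On pro-BNP, one can say that three places require the test and one footnote omits it, so this is a schedule error and not a missing measurement. That is right, and a reader who inferred that the plan forgets follow-up pro-BNP altogether would be wrong. It does not remove the risk, because the schedule is a natural working document for the person drawing blood.

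On Post Visit #2, the two readings are not equally supported. Appendix A's numbering favours the conditional visit, and Section 9.3 can serve both post-treatment office visits, so the existence of Sections 9.3 and 9.4 does not itself point to Day 30. This stands. It narrows the ambiguity, but the two Synopsis sentences still leave it open and no text closes it.

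Three stronger readings are tempting, and the documents do not support them:

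- *Both endpoints are undefined as a whole.* Only the Post Visit #2 part is open. Post Visit #1 already describes all patients assessed after the initial course, and no section presents Post Visit #2 as the effect in all treated patients.
- *The extension percentage pools success with failure.* Its numerator is patients given the extra 4 days and pools nothing. Only its complement is mixed, and no section treats that complement as success. Treatment failure is a listed withdrawal reason in Section 6.3, and 30-day heart failure hospitalization and events are endpoints.
- *A smaller Post Visit #2 group means a loss of planned precision.* Section 14 plans means with SD, medians with IQR, and percentages. It plans no confidence interval for weight change.

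**Conclusion.** Two corrections are warranted.

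1. **Appendix A contradicts Sections 9.3 and 9.4 and the Synopsis on pro-BNP at three clinic visits.** This rests on the text alone. At a site that followed the footnote literally, every patient would lack the follow-up value for a primary endpoint. How many sites would do so cannot be known from the documents.
2. **Post Visit #2 is not tied to a visit.** The conditional second post-treatment visit is the closer match and Day 30 the weaker one. The readings differ in timing and in patients: 12 to 36 against up to 60, if 20% to 60% are extended. Under the closer reading, the result describes patients who responded and still needed parenteral diuretics, and should be labelled so. The extension shares and weight means above are assumptions; the gap in definition does not depend on them.

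The mixed complement of the extension percentage is not an error. A fuller table would help interpretation, as a reporting suggestion only. The sample-size statement is unaffected.

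**What to change.** 1. **Appendix A.** List pro-BNP, for example as its own row, at baseline, First Post Treatment, Second Post Treatment and Day 30. Leave it off the home treatment days, where Section 9.2 does not list it.
2. **Section 10.1 and the Synopsis.** Name the Appendix A column for Post Visit #1 and for Post Visit #2, and report the number of patients at each.
   - If #2 is the conditional visit, present it as the extended subset beside the same patients' Post Visit #1 values. Optionally add the change to the end-of-treatment visit in all treated patients (First Post Treatment, or Second Post Treatment if extended), noting that it mixes 3-day and 7-day courses.
   - If #2 is Day 30, report how many patients had rescue treatment before it.
3. **Optional.** Beside the extension percentage, show day-3 disposition for all treated patients in exclusive categories: finished at 3 days; extended; withdrawn or admitted without response; other.

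The cost is a few lines of wording and some table shells. No visit is added, and no test beyond those Sections 9.3 and 9.4 already require. The label should be settled before the data are examined.

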10.2 Safety Endpoints

- The safety of the sc2 Wear furosemide drug-device combination will be assessed by the incidence of adverse events.
- Discontinuation due to presence of skin reaction to drug or device/adhesive.

11 RISK MANAGEMENT

Furosemide has been available for over five decades and is considered a safe drug. The potential risks related to this study are not different from the risks of any form of diuresis whether inpatient or outpatient. During diuresis, sometimes there are rapid fluid shifts which could lead to electrolyte imbalance or postural hypotension. Subjects will be closely monitored and electrolytes will be supplemented as needed. Patients will be encouraged to avoid rapid postural changes during diuresis and will need to be homebound to ensure their safety.

Patients will be informed of the expected increased urine output. Rarely gout may also be precipitated when fluid is taken out of the body. Dryness of the mouth, thirst, weakness, lethargy, drowsiness, restlessness, muscle pains or cramps, muscular fatigue, hypotension, oliguria, tachycardia, arrhythmia, or gastrointestinal disturbances such as nausea and vomiting will be monitored. There are rare risks of local allergic reaction from the adhesive of the infusor, activation of systemic lupus erythematosus or worsening kidney function in which case the SQ furosemide infusion will be stopped. Patients allergic to sulfa may be allergic to furosemide. Patients with diabetes mellitus should be told that furosemide may increase blood glucose levels and thereby affect urine glucose tests. The skin of some patients may be more sensitive to the effects of sunlight while taking furosemide. Patients may not participate in this study if they are pregnant or plan to be pregnant during the study since the effects of the study device system on an unborn baby are unknown.

12 SUMMARY OF BENEFITS

It is anticipated that patients will experience clinical improvement of the symptoms and signs of HF. Participants will also avoid the cost related to being admitted to the hospital for intravenous furosemide infusion.

13 PARTICIPANT SAFETY AND ADVERSE EVENTS

Adverse Events

An adverse event (AE) is any unfavorable or unintended medical occurrence associated with the use of an investigational product (IP). This does not necessarily imply causality. Pre-existing conditions would be reported as AEs if the frequency, intensity, or character of the pre-existing condition worsens during the course of the study. Conditions detected after use of the IP are AE, though they might have prior existence. Laboratory or functional test abnormalities that meet the criteria for AEs are those that are associated with clinical signs or those whose clinical symptoms require medical intervention, and or which require the IP to be discontinued. When the patient withdraws from the study

13.1 Suspected Adverse Reactions

A suspected adverse reaction (SAR) refers to events which could have been possibly caused by the drug. Adverse reactions, a subset of SAE, indicates a higher certainty (that event was caused by IP).

